# C. Study Design and Research Methods

## Study Design:

This study will be a prospective non-randomized cohort study with patients presenting to Children's Hospital Colorado for resection of a central nervous system tumor. Due to heterogeneity of the pediatric central nervous system tumors and the evidence available, we will have a planned initial cohort (first phase) that will include tumor pathology that will allow us to test the feasibility of the study and the preliminary activity of fluorescein in the pediatric population. After completion of this initial cohort, we will expand our study to include tumors that are more specific to the pediatric population.

Currently, there exist many tumor types where there is robust literature on the use of fluorescein [3,4,6-15,21-26,27-29]. We plan to enroll patients based on a phased system and after completion of the first phase, we will perform a safety analysis as outlined below.

[name]: 18-0242 Page 3 Version: 07/03/2019

After safety analysis is completed, we will either proceed to the next phase, or in the event there is a safety concern, the DSMC will terminate our study. Terms for termination are detailed below.

Enrollment of ten patients is planned for each tumor type in each of the phases. The phases are designed to assess patients where evidence is available and proceed to tumor types where pediatric evidence is limited and the tumors are more unique to the pediatric population. This will allow us to safely assess patients and allow us to expand our trial in a controlled fashion. After completion of each phase of enrollment, we will continue enrolling the prior phase patients for a maximal total of 10 patients per each pathology group. Thus, maximal enrollment will be 20 patients for the first phase pathologies and 30 patients for the second phase pathologies, for a total enrollment of 50 treated patients and 150 historical controls

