[name]: 18-0242 Page 6 Version: 07/03/2019

physical, neurologic exam data, and may also include laboratory findings and post-operative imaging studies. These will all be documented clinically and recorded via chart review for the study. Patients will be followed for the study through Month 2 (or 8 weeks) post-surgery.

Furthermore, any adverse events occurring after surgery will be collected until 7 (for non-serious AEs) or 30 days (for SAEs) after the last day of study intervention (administration of fluorescein). All adverse events will be followed for outcome information until resolution or through Month 6 post-surgery.

For example, if a patient has no adverse events following surgery, they will only be followed through end of study period which is 2 months post-surgery. If the patient had adverse events within the first 30 days, those adverse events will be followed through resolution or 6 months post procedure, whichever comes first.

Re-Enrollment: Patients who have previously been enrolled in this study and received prior administration of fluorescein sodium as a part of this study for guided tumor resection are eligible for re-enrollment into the study, should further surgical resection be clinically indicated. Patients will receive the same dosage as outlined in the protocol of 3mg/kg. Clearance of 500mg of fluorescein sodium is 24-72 hours after administration of a single dose [16]. Patients re-enrolled into the study will be eligible after 3 days given the clearance time necessary for fluorescein sodium. Patients will be enrolled with the same study number. Patients will be reconsented at time of re-enrollment.

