Given this, we propose a 3:1 ratio of historical controls to fluorescein treated patients to match tumor location and histology. 150 historical controls will be pulled from the last ten years of Children's Hospital patients and matched to the 50 fluorescein treated cases on lesion location and pathology. This 3:1 ratio will strengthen our ability to objectively assess for adverse events related to sodium fluorescein as well as our extent of tumor resection analysis. Importantly, historical controls undergo stereotactic-guided tumor resection in a similar fashion to patients undergoing fluorescein administrations as outlined in our protocol.

All patients who undergo sodium fluorescein-aided resection will also have neuropathological analysis. We will analyze correlation of fluorescein staining to histopathology. Tissue obtained during the time of surgery will be used to correlate fluorescein staining to histopathological diagnosis. This data will be used to calculate sensitivity and specificity of fluorescein staining for tumors. Pre- and post-operative imaging will be used to assess the degree of the extent of resection in intraparenchymal tumors. Data collected from post-operative follow-up will be used to assess for potential complications/adverse reactions associated with sodium fluorescein administration.

For data analysis, extent of tumor resection will be compared as a continuous value across groups using a parametric ANOVA. Further calculations, such as sensitivity, specificity and positive predictive value will be calculated by contingency tables. Additionally, since group membership is not random we will run an adjusted analysis predicting the likelihood of tumor resection as a continuous outcome adjusting for demographic and co-morbidity factors. Significance will be assigned at p < 0.05.

Furthermore, adverse reactions and population/demographic data will be characterized using relative risk and odds ratios. Overall survival and progression free survival analysis will be characterized using Kaplan-Meier curves and compared across groups using a log rank test.

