## e. Time Period and Frequency for Event Assessment and Follow Up

21 CFR 312.64(b) requires that the Site Principal Investigator records non-serious adverse events and reports them to the Sponsor according to the timetable for reporting specified in the protocol.

A properly delegated study team member will record all adverse events with start dates occurring any time after administration of fluorescein until 7 (for non-serious AEs) or 30 days (for SAEs) after the last day of study intervention. All events will be followed for outcome information until resolution or stabilization or through Month 6 post-surgery.

All AEs occurring while on study will be documented regardless of their relationship to the study intervention, and whether or not they meet the definition of an SAE. AEs will be captured, reviewed and assessed by an LIP member of the study team. The outcome of this review and assessment will be documented by a properly delegated study team member on an Adverse Event Log. Information to be collected includes event description, time of onset (start date) and time of resolution/stabilization of the event (end date), and the LIP's assessment of expectedness, severity and relationship to study intervention.

Any medical condition that is present at the time the participant is screened will be considered as baseline medical history, and will not be recorded as an AE. However, if the study participant's condition deteriorates at any time during the study, the event will be recorded as an AE.

Changes in the severity or frequency of an AE will be documented as separate events to allow an assessment of the duration of the event at each level of severity or frequency.

AEs characterized as intermittent will be documented with onset and duration of each episode.

At each study visit, a properly delegated study team member will document all occurrences of AEs and SAEs since the last visit. This information will be gathered through direct observation (e.g. rash), elicited from or spontaneously volunteered by the participant, documentation in Medical Records, laboratory or other clinical reports or notes, or identified in patient-reported outcome tools (e.g. diaries, surveys, questionnaires), or any other means.

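### The adverse-event relative risks set prospectively collected events in treated patients against historical controls with no stated collection method, so they cannot separate a fluorescein effect from a difference in detection.

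*Combined protocol and SAP*

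**What the plan says.** **The comparison.** Section IV.C (Study Design) plans enrolment "for a total enrollment of 50 treated patients and 150 historical controls". Section IV.F says that "150 historical controls will be pulled from the last ten years of" the hospital's patients and "matched to the 50 fluorescein treated cases on lesion location and pathology". It gives adverse-event assessment as one purpose of the ratio: "This 3:1 ratio will strengthen our ability to objectively assess for adverse events related to sodium fluorescein". The analysis is that "adverse reactions and population/demographic data will be characterized using relative risk and odds ratios". This sentence names no comparator, but the historical controls are the only other group.

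**Treated patients.** Section IV.G.1.e has study staff document events at each visit: "This information will be gathered through direct observation (e.g. rash), elicited from or spontaneously volunteered by the participant", with medical records and clinical reports as further sources. A licensed practitioner assesses each event and it goes on a log. On scope, "All AEs occurring while on study will be documented regardless of their relationship to the study intervention". Collection runs from fluorescein administration for 7 days (non-serious) or 30 days (serious), as also stated under Follow-Up in section IV.C. In Table 1 the adverse-event row does not carry the mark for chart-review data. Section IV.G.1.f lists disease-related events, among them bleeding, infection, seizures, cerebrospinal fluid leak and stroke, that are not reported through the standard adverse-event process.

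**Controls.** No section says how, by whom, over what window or against what event list their adverse events are counted. Section IV.F describes historical follow-up as reliable, but only for post-operative neurologic reactions. The adjusted analysis there is for extent of resection.

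**The concern.** A relative risk for harm can be interpreted only if an event of a given kind has the same chance of being counted in each group. Here that chance differs for at least two reasons, and they pull in opposite directions. Asking and observing at each visit finds minor events that a routine chart from years ago may not hold, which raises the ratio. Taking common surgical complications out of the standard process for treated patients, with no matching rule for controls, could lower it.

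Matching on location and pathology does not address detection, and neither does the resection-only adjustment. The limitations in section IV.E cover the single site and the lack of randomization, not how events are found. At stake is the plan's only between-group safety comparison, in children. A raised ratio could suggest harm, and a low one could reassure, when neither reflects the dye.

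**Working it through.** **The plan's own figures.** No rate, power or precision is stated for adverse events, so there is no safety figure to reproduce. The only sample-size figures are in Table 3 (total N of 64, 80 and 106 for 70%, 80% and 90% power). They reproduce with a two-sided two-group comparison, difference 16, SD 25, alpha 0.05. They concern resection and do not bear on this point.

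**Inputs.** From the documents: 50 treated, 150 controls. Assumed, because the documents do not give them: the true event rate (the same in both groups, so the true relative risk is 1), the share of events counted in each group, and a two-sided pooled z test at 0.05.

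**Formula.** Observed RR = true RR × (share counted in treated ÷ share counted in controls).

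**A. Controls under-counted, treated fully counted, true rate 20%.** Treated: 50 × 0.20 = 10 expected events. Controls: 150 × 0.20 = 30 true events.
- 80% counted: 24 of 150 = 16%. RR = 0.20/0.16 = 1.25. Odds ratio = (0.20/0.80)/(0.16/0.84) = 1.31.
- 60% counted: 18 of 150 = 12%. RR = 0.20/0.12 = 1.67. Odds ratio = (0.20/0.80)/(0.12/0.88) = 1.83.

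Chance of p < 0.05 with no true effect, by exact enumeration of all 50 v 150 tables:

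| True rate | 80% counted | 60% counted |
|---|---|---|
| 5% | 7% | 13% |
| 10% | 9% | 19% |
| 20% | 10.9% | 30.6% |
| 30% | 14.7% | 44.3% |

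With equal counting at the 20% rate it is 4.9%. With 90% counted in controls at that rate it is 6.6%. Fisher's exact test at the 20% rate gives 9% and 26% in place of 10.9% and 30.6%.

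**B. Treated under-counted, controls fully counted, true rate 20%.** This stands for the carve-out of disease-related events.
- 75% counted: 15% v 20%. RR = 0.75, p < 0.05 in 10%.
- 50% counted: 10% v 20%. RR = 0.50, p < 0.05 in 35%.

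**C. Do more controls help?** Standard error of log RR = √[(1−p₁)/(n₁p₁) + (1−p₀)/(n₀p₀)]. At 20% in both groups with equal counting, the 95% interval around RR 1 is 0.46 to 2.19 with 50 controls and 0.53 to 1.90 with 150. That is a gain in precision only. With 60% counted in controls, the ratio centres on 1.67 whatever the number of controls. The chance of a false p < 0.05 rises from 31% with 150 controls to 39% with 1,000, because the interval tightens around the wrong value.

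**The case against.** - **The contrast is not absolute.** Medical records are one of the treated patients' event sources, and their follow-up evaluations are recorded by chart review. That controls are chart-only is an inference, since the plan is silent. This stands, and it narrows the gap. It does not close it: past patients cannot be asked or observed prospectively, and treated patients will be.
- **The ratio is descriptive.** The plan says adverse reactions will be characterized and names no test for them, and the p < 0.05 rule closes the paragraph on resection and diagnostic accuracy. This stands, so the rejection rates above only indicate size. The shift in the ratio does not depend on a test.
- **Safety decisions rest elsewhere.** The monitoring committee reviews events directly and must approve the second phase. This stands and limits the consequence to the reported comparison.
- **The inputs are assumed.** This stands. At low event rates or high chart capture the distortion is small.

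A reader might also infer that the treated window contradicts itself, 7 or 30 days in one place and the whole time on study in another. The documents do not support that reading. The Follow-Up text and section IV.G.1.e both give 7 and 30 days, and the sentence on events while on study concerns scope (any relationship, any seriousness).

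**Conclusion.** The point holds in a limited form. As written, the relative risks and odds ratios cannot separate a fluorescein effect from a difference in how events were found, and the 3:1 ratio improves precision, not objectivity. The direction is unknown. Under the assumed inputs at a 20% rate, the ratio could sit at 1.25 to 1.67 if controls are under-counted, or 0.50 to 0.75 if treated patients are, with no true effect.

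A reader might go further and conclude that the ratio reflects detection rather than safety, or that it must overstate harm. Neither follows. The documents give no event rates or capture shares, the carve-out could push the ratio down, and events charted reliably in both groups, such as death or reoperation, are less affected. The change should be made, but it does not undermine safety oversight of the study.

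**What to change.** In section IV.F:
1. Compute relative risks and odds ratios only on events abstracted from the medical record in the same way in both groups: one event list that includes the disease-related events of section IV.G.1.f, one abstraction form, and one window counted from surgery or induction of anaesthesia (for example the plan's own 30 days).
2. Report prospectively elicited events in treated patients descriptively, without a ratio.
3. Name the historical controls as the comparator, and either delete the claim of objectivity or say that the 3:1 ratio improves precision only.

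The cost is analysis wording and chart abstraction on one form for both groups. No new patients, visits or tests are needed, and safety reporting and committee review are unchanged. The downside is that minor events that charts do not record are described but not compared.

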#### IV. Research Methods

### A. Outcome Measure(s):

The primary outcome measure will be extent of tumor resection. For all patients, pre-operative imaging and post-operative imaging will be used to analyze the extent of resection of the tumors. In intracranial lesions, the use of volumetric imaging tools will be used to calculate the extent of tumor resection. In spinal lesions, manual measurement will be used to determine the extent of resection.

Secondary outcome measures include the subjective utility of fluorescein per the operating surgeon, as well as positive predictive value, sensitivity and specificity for extent of tumor resection. Additional outcome measure(s) will vary depending on the neurosurgical tumor removed. Intraoperative videos and images will be collected from the surgical case. Images obtained will be correlated to tissue biopsy and will aid in the analysis of fluorescein

[name]: 18-0242 Page 2 Version: 07/03/2019

extravasation in pediatric neurosurgical tumors. All tissue samples collected will be taken for histopathological analysis.

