# F. Data Analysis Plan:

Annually at the Children's Hospital of Colorado, roughly 80 patients present with tumors requiring neurosurgical interventions. Prior adult population studies had enrolled between 10 – 40 patients. Importantly, these studies have largely involved single tumor types. Our study involves multiple tumor types and locations and would warrant increased enrollment for statistical analysis. Additionally, extent of surgical resection is an important outcome in our project. Using data extrapolated from adult studies, such as the most recent Niera et al. study, 32 patients were enrolled and compared to historical controls for tumor resection. This study demonstrated differences in extent of resection. Given the population and nature of our study, about 1/10 of the patients whom qualify for this study will be spine patients and the rest will be cranial with varying types of tumor pathology. [19]

Furthermore, if we use the number from this study [Niera] patients with fluorescein use had an average resection rate of 93.1% versus 77.1% for non-fluorescein historical control patients [19] Power calculations using a one-way ANOVA with alpha=0.05 power at 70%, 80%, and 90%, a mean difference of 16% (93.1-77.1) and a standard deviation of 25% are shown in Table 3.

Table 3: Power Calculation			
Power	N Total		
70%	64		
80%	80		
90%	106		

[name]: 18-0242 Page 8 Version: 07/03/2019

Our pediatric neurosurgery/ neuro-oncology program benefits from a robust tumor program with multiple historical patients with reliable clinical follow-up that assesses for post-operative neurologic reactions. However, we do not believe that randomization is feasible in our study. The overall prevalence of pediatric brain tumors and the nature of the pathology would not allow our center the ability to perform a randomized trial in a meaningful time-frame. Our trial is designed to be a multi-year trial and randomization would double the study time for enrollment and greatly decrease feasibility to perform this study.

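### Controls are matched on tumour location and pathology, but no planned model contains those factors, and Table 3 gives power for equal groups, not the planned 50 v 150

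*Combined protocol and SAP*

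**What the plan says.** Section IV.C (Study Design) plans ten patients for each of five tumour types, "for a total enrollment of 50 treated patients and 150 historical controls". Section IV.F says that the controls come from the last ten years at the hospital and are "matched to the 50 fluorescein treated cases on lesion location and pathology".

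For the primary outcome, IV.F states that "extent of tumor resection will be compared as a continuous value across groups using a parametric ANOVA". It adds that, because patients are not randomised to the two arms, "we will run an adjusted analysis predicting the likelihood of tumor resection as a continuous outcome adjusting for demographic and co-morbidity factors". Neither sentence names location, pathology or the matched set.

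The sample size basis in IV.F is a one-way ANOVA with alpha 0.05, a mean difference of 16 points (93.1 minus 77.1) and a standard deviation of 25 points. Table 3 gives total numbers of 64, 80 and 106 for 70%, 80% and 90% power. It states no allocation ratio. The 3:1 ratio is introduced after the table, and no power is given for it.

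**The concern.** Matching on a factor that predicts the outcome makes the two groups alike on it. The true sampling error of the group difference then falls. An analysis that leaves the factor out still counts the variation between strata as error, so it overstates the standard error. The precision that matching provides is lost.

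The documents give reason to expect strata to differ. IV.F says "Our study involves multiple tumor types and locations and would warrant increased enrollment for statistical analysis". IV.A uses volumetric tools for intracranial lesions, but "In spinal lesions, manual measurement will be used to determine the extent of resection", so even the method of measurement changes with location.

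At stake are the width of the primary confidence interval and the power to detect a difference smaller than 16 points. That figure is carried over from one adult study with historical controls. The point here is variance only. Bias from non-randomised historical controls is a separate matter.

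The second issue is that a reader who takes Table 3 as the justification for this trial is reading figures for a different allocation.

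**Working it through.** **Inputs from IV.F:** difference 16, SD 25 (variance 625), alpha 0.05 (taken as two-sided, as the F test of two groups is), 50 treated and 150 controls. **Assumptions:** the share *f* of variance between tumour types, varied from 0 to 40%; a smaller difference of 10 points as an illustration.

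**1. Reproducing Table 3.** Power comes from the noncentral t distribution with n1 + n2 − 2 degrees of freedom and noncentrality (16/25) / √(1/n1 + 1/n2).

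- 32 v 32: 0.64/0.2500 = 2.56, power 71.2%
- 40 v 40: 0.64/0.2236 = 2.86, power 80.7%
- 53 v 53: 0.64/0.1943 = 3.29, power 90.4%

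These are the smallest equal-group totals that reach 70, 80 and 90%, so all three rows match exactly. A one-sided test with equal groups would give 48, 62 and 86, which does not match.

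**2. The same calculation at 3:1.**

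| Target power | Table 3 total | Power of that total split 3:1 | Total needed at 3:1 |
|---|---|---|---|
| 70% | 64 | 58.8% | 84 (21 v 63) |
| 80% | 80 | 68.7% | 108 (27 v 81) |
| 90% | 106 | 80.7% | 140 (35 v 105) |

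For 50 v 150, √(1/50 + 1/150) = 0.1633 and 0.64/0.1633 = 3.92. Power is 97.4% at 16 points, 80% at 11.5 points and 68.4% at 10 points.

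**3. Effect of leaving out the matching factors.** With three controls per case within each type, differences between types cancel from the group comparison. The true standard error is 25 × √(1 − *f*) × 0.1633 = 4.082 × √(1 − *f*). The ANOVA estimates about 4.082 whatever *f* is. The ratio is 1/√(1 − *f*), that is 1.05, 1.12, 1.20 and 1.29 for *f* = 10, 20, 30 and 40%.

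A simulation with normal data, five types, 10 v 30 in each, total variance 625 and 100,000 runs per cell gives the following (repeat runs agree to about 0.3 points):

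| *f* | ANOVA type I error | Power at 10 points, ANOVA v strata | Power at 16 points, ANOVA v strata |
|---|---|---|---|
| 0% | 5.0% | 68.3 v 68.3% | 97.4 v 97.4% |
| 10% | 4.0% | 69.2 v 73.0% | 97.9 v 98.4% |
| 20% | 2.8% | 70.4 v 77.9% | 98.4 v 99.1% |
| 30% | 2.0% | 71.4 v 83.1% | 99.0 v 99.7% |
| 40% | 1.2% | 72.9 v 88.3% | 99.4 v 99.9% |

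With strata in the model, the type I error stays at 5.0% throughout.

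**4. Difference detectable with 80% power.** For the ANOVA it is 1.972 × 4.082 + 0.842 × 4.082 × √(1 − *f*), which gives 11.3, 11.1, 10.9 and 10.7 points at *f* = 10, 20, 30 and 40%. With strata (noncentral t, 194 degrees of freedom) it is 10.9, 10.3, 9.6 and 8.9 points.

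**The case against.** The strongest reply is that little is lost on the protocol's own inputs. At 16 points the cost is 0.5 to 0.7 points of power, and the error is on the conservative side. A visible loss needs two figures that the documents do not give: a difference near 10 points and a material share of variance between types. At a 10% share, the loss at 10 points is under 4 points of power. All of this is right and limits the weight of the point. The interval is nevertheless too wide whatever the true difference.

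On Table 3, the planned 200 exceeds the 140 needed for 90% power at 3:1. The table is correct for equal groups, and nobody plans to split its totals 3:1. That also stands: this is a gap in documentation, not a shortage of patients.

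The wording of the analysis does not strictly exclude a multi-factor ANOVA, since one-way appears only in the power calculation. But no other factor is named, and the adjusted model's stated covariates leave out both matching factors.

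The simulation is idealised. Extent of resection cannot exceed 100%, so normal data with SD 25 around a mean of 93.1 is not realistic, and the decimals should not be over-read. Types may be uneven: ten per type is a maximum, and IV.F expects about one tenth of patients to have spinal tumours, roughly 5 of 50. Location levels are not defined, so cells formed by crossing type and location could be sparse. In a check with uneven types and five extra location terms, the cost was only about 1 point of power when the strata explained nothing.

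**Conclusion.** The concern holds, as an improvement that should be made and not as a fatal fault. The plan matches on location and pathology and then names neither in any model. If strata differ, the primary test is conservative and its standard error too large, by about 5 to 29% for assumed between-type shares of 10 to 40%. The consequence is negligible at 16 points and becomes relevant near 10 points, where power falls short by about 4 to 15 percentage points. These sizes rest on an assumed variance share, normal data and balanced matching; with a share of zero the two analyses perform alike.

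That Table 3 assumes equal groups is inferred from its numbers, but the inference is firm: all three rows match at 1:1 and none at 3:1. The planned 50 v 150 is adequately powered on the protocol's inputs. Table 3 simply does not say so.

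**What to change.** Replace the primary analysis sentence in IV.F with wording such as:

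> Extent of resection (%) will be compared between groups with a linear model containing group and the matching factors (tumour type and lesion location). The group difference with its 95% confidence interval is the primary result. The unadjusted ANOVA is a sensitivity analysis.

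Add tumour type and location to the covariates of the adjusted analysis. Use the location levels applied in the matching, write them down, and say how sparse levels will be combined; entering the two factors as main effects avoids small crossed cells. Heteroscedasticity-robust standard errors are optional.

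Replace Table 3 with:

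> With 50 treated patients and 150 matched controls, SD 25% and two-sided alpha 0.05, power is 97% for a 16-point difference and 80% for an 11.5-point difference.

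State that these figures are for the unadjusted comparison. They are conservative for the model above if the strata explain variance.

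The cost is wording, including a short definition of the location levels. Both factors must already be known for every case and control, because they are what the controls are matched on. No extra patients or data are required.

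### The pooled-variance ANOVA planned for percent resection (50 treated, 150 controls) will probably give too wide an interval, because the plan's own means make a common SD of 25% implausible

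*Combined protocol and SAP*

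**What the plan says.** Section IV.A names the endpoint: "The primary outcome measure will be extent of tumor resection". It is measured by volumetric imaging for intracranial lesions and by hand for spinal ones.

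Section IV.F takes its planning means from an adult study in which "fluorescein use had an average resection rate of 93.1% versus 77.1% for non-fluorescein historical control patients", and then states that power for "a mean difference of 16% (93.1-77.1) and a standard deviation of 25% are shown in Table 3". Table 3 lists total sizes of 64, 80 and 106 for 70%, 80% and 90% power.

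The same section sets the comparison group: "150 historical controls will be pulled from the last ten years of Children's Hospital patients and matched to the 50 fluorescein treated cases". The primary test is given in these words: "extent of tumor resection will be compared as a continuous value across groups using a parametric ANOVA". An adjusted model for the same continuous outcome follows. The rule for both is "Significance will be assigned at p < 0.05".

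The plan names no unequal-variance, rank-based, transformed or bounded-outcome method and no check of assumptions. It does not use the words equal variance, but a one-way ANOVA planned with a single SD implies it.

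**The concern.** An ordinary ANOVA estimates one variance from both groups together. When the groups differ in size and in spread, that pooled figure is mostly the variance of the larger group, and the standard error of the difference is wrong even in large samples. Here the controls outnumber the treated three to one.

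Percent resection has a ceiling at 100, so a group whose mean is close to 100 has little room to vary. If fluorescein performs as the plan hopes, the treated group sits nearer the ceiling than the controls and should have the smaller SD. The pooled interval would then be wider than the data justify. Section IV.E describes this as a pilot leading to a multi-site study, so the width of the interval is a result in itself, because it informs the size of the next trial.

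**Working it through.** **Inputs from the documents.** Means 93.1 and 77.1, difference 16, one SD of 25, alpha 0.05 (section IV.F). Group sizes 50 and 150 (sections IV.C and IV.F).

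**Assumed.** Treated SD of 10 to 20 with control SD 25. The documents give no SD per group.

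**Step 1: reproduce Table 3.** Standardised effect = 16/25 = 0.64. A two-sided equal-variance t test with two equal groups gives totals of 64, 80 and 106, an exact match. Table 3 therefore rests on a common SD and 1:1 groups. With 50 and 150 and a common SD of 25, power is 97%.

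**Step 2: limit on the SD.** A variable on 0 to 100 with mean m has SD at most √(m(100 − m)).
- Treated: √(93.1 × 6.9) = 25.35.
- Control: √(77.1 × 22.9) = 42.02.

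An SD of 25 at mean 93.1 is below the limit, but only just, and it needs a nearly all-or-nothing outcome. A beta distribution with that mean and SD puts about 93% of children above 95% resection and about 6% (3 of 50) below 5%.

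**Step 3: pooled against true standard error.**
- Pooled SE = √{[(49s² + 149 × 625)/198] × (1/50 + 1/150)}
- True SE = √(s²/50 + 625/150)

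For s = 10: pooled variance = (4,900 + 93,125)/198 = 495.1, so pooled SE = √(495.1 × 0.02667) = 3.63. True SE = √(2 + 4.167) = 2.48. Ratio 1.46.

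| Treated SD (assumed) | Pooled SE | True SE | Excess | Coverage of nominal 95% interval |
|---|---|---|---|---|
| 10 | 3.63 | 2.48 | 46% | 99.5% |
| 12 | 3.67 | 2.66 | 38% | 99.2% |
| 15 | 3.75 | 2.94 | 27% | 98.7% |
| 20 | 3.90 | 3.49 | 12% | 97.4–97.6% |

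Coverage comes from simulated trials of 50 and 150 with beta-distributed outcomes at the plan's means (at least 20,000 per scenario). Welch intervals in the same trials covered about 94% to 95%.

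**Step 4: power (simulated, control 77.1 with SD 25).**

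| Treated mean | Treated SD | ANOVA | Welch |
|---|---|---|---|
| 93.1 (planned) | 10 | >99.9% | 100% |
| 93.1 (planned) | 15 | 99.8% | 99.8% |
| 93.1 (planned) | 20 | 98.3% | 97.6% |
| 85 (assumed) | 10 | 63% | 89% |
| 85 (assumed) | 15 | 58% | 75% |
| 85 (assumed) | 20 | 54% | 61% |

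**Step 5: type I error when both groups share one distribution (simulated).** ANOVA: 5.0% at mean 77.1, SD 25, and about 5% at mean 93.1, SD 12. Welch: 5.4% and 5.8% to 6.0%, rising to between 6% and 7% at mean 93.1, SD 20.

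**The case against.** A reader might go further and infer that the plan's means rule out a common SD of 25%, or that the primary p-value is invalid. The documents support neither. The limit at 93.1% is 25.35, so 25 is allowed. If fluorescein does nothing and both groups share one distribution, the ANOVA keeps its 5% level.

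A reader might also fear false positives. With equal means of 90, a treated SD of 20 and a control SD of 10, the ANOVA rejects about 15% of the time. That is the opposite of the variance pattern that the plan's means suggest, and nothing in the documents points to it.

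The strongest objection is that nothing material is lost at the only effect the plan is built on: both tests have about 98% power or more at 16 points. The losses at a treated mean of 85 depend on an assumed difference of 7.9 points. There the ceiling no longer forces a small SD (limit √(85 × 15) = 35.7), and at treated SD 20 the gap is only 7 percentage points. The remedy also has a cost, since Welch is slightly anti-conservative in strongly skewed data.

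All of this stands, and it lowers the severity. It does not remove the point: the interval is still likely to be miscalibrated, the 16 points are borrowed from adults, and the plan names no alternative for either the simple or the adjusted analysis.

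**Conclusion.** The concern holds in a limited form. Under the plan's own means, equal variances are implausible though not impossible, and the treated SD is probably the smaller. The pooled standard error would then be about 12% to 46% too large and the 95% interval would cover about 97.5% to 99.5%, given a treated SD of 20 to 10 and a control SD of 25. These SDs are assumptions and set the size of the effect.

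The direction is conservative. The cost is an interval that is too wide and, if the true difference is well below 16 points, some loss of power. Severity is minor to moderate; the primary conclusion is not invalidated.

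**What to change.** In section IV.F:

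1. Replace the parametric ANOVA with an unequal-variance (Welch) comparison for the simple analysis, and specify heteroscedasticity-consistent (HC3) standard errors for the adjusted model.
2. Name one sensitivity analysis for the ceiling: a permutation test or a fractional-logit model.
3. State the SD assumption beside Table 3 per group, as a range. The control SD can be taken from the ten years of charts that supply the controls.

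The cost is wording and a software option. No patients are added and the sample size does not change: the plan already has 50 + 150 = 200, against a largest Table 3 total of 106. The downsides are slightly fewer degrees of freedom and a type I error for Welch of about 6% to 7% when both groups share a strongly skewed distribution. The permutation test guards against the latter, which is a reason to prefer it as the sensitivity analysis. The choice should be fixed before outcome data are compared, so that the primary test is not picked after the variances are seen.
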